#### **Ethical considerations**

This study's approval for ethical clearance will be obtained from Jawatan Kuasa Etika Perubatan (JKEP) University Putra Malaysia (UPM) and National Medical Research Register (NMRR); Medical Research and Ethics Committee (MREC) as the participants will be working in Ministry of Health facilities during the 1 month follow up. This study will also be registered in the National Institute of Health (NIH) as a trail registration.

Informed consent will be obtained from each study participant and they will be told the right not to respond to the questions they don't want to respond to or to withdraw from the study at any time. All data obtained will be kept confidentially and for research purposes only.

The benefits of the study includes assessing issues in relations to HO wellbeing and to assess what is needed in training a functional HO. The potential risk, discomforts and inconvenience is almost none. However, should the DASS score be suggestive of depression or anxiety, team members of the research team will refer the participant appropriately. Should participants choose to withdraw from study, they will be allowed to do so.

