#### LITERATURE REVIEW

#### Current Housemanship (HO) Scenario Worldwide and in Malaysia

Reduced psychological well-being amongst House Officers (HOs) is a known worldwide issue. For example in Norway, 11% of house officers are reported to have mental health problems needing treatment. (Tyssen, Vaglum, Gronvold, & Ekeberg, 2000). In the UK (Midlands), 46% is said to have clinical depression (J Firth-Cozens, 1990). The numbers don't run far amongst local Malaysian studies where it is said to be at a range of around 31-58% reported on various psychological conditions.

For example 31% of HOs are reported to be distressed, 36.6% indicates a high level of emotional burn out and the level of stress to be 34% in Kuala Lumpur and as high as 58% in Kota Kinabalu. (Al-Dubai et al., 2013; Shahruddin et al., 2016; Yusoff et al., 2011)

There many consequences of this psychological impact towards the HOs themselves, the healthcare system and towards the nation as a whole. Among the direct impact of stressed HOs is the number of them completing training within the allocate two years has been decreasing from 86.4% in 2009 to only 58.8% in 2012.(Lim, 2017) The dropout rate, which is defined as HOs not completing their training within 5 years is said to be slowly increasing from 3.7-4.8% per batch year.

A high level of stress is related is likely to affect thoughts of quitting HOship by up to three times, as evidenced in 2016 where 1.2% of HOs were either terminated or quit due to the inability to cope with stress. (Lim, 2017; Shahruddin et al., 2016)

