### Intervention:

The intervention in this study will be the Medicorp HO preparatory course which comprises of a 3 day training touching on aspects of HO training that is needed practically for a HO to function. The training will touch on the nature of the HO job, explaining about technical details such as the shift and on call system. The tagging period, and assessments that HOs need to undergo during their training. They will be guided on how to clerk, review and present common as well as emergency cases. Other aspects involved in clerking such as common forms used in the wards and also how to refer cases is also discussed. Apart from that, soft skills such as communication among staff, financed, balancing social life and future career planning is incorporated in the training. There are hands on training for participants for common procedures such as continuous bladder drainage insertion and venepuncture. The trainers are specialists, specialists in training, medical officers, and also house officers who come to share their experience. Medicorp encourages their alumni to be part of their training program. This module will be held on a 1-2 monthly basis. The Module Content is moderated by Medicorp based on discussions with board of directors, advisors and feedback from participants. The training program are done as lecture, tutorial and hands on session. Before commencing the course, participants will be included in a whatsapp group, for easier content sharing and updates of the course. They will continue this networking even after completion of this course. They will be also be guided in the online applications of their job through this application and also through Facebook. During the commencement of their job, Medicorp will use their database to guide them into different whatsapp groups according to their place of work for additional support.

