#### 2. Secondary outcome

a. Readiness

This is also adapted from the IMU competency survey and is asked on a likert scale of 1 to 5 for their level of readiness. It is assessed after the confidence section. The higher the score, the higher the level of readiness.

b. Psychological wellbeing

This is using the Depression Anxiety Stress Scale (DASS): This questionnaire is used to asses Depression, Anxiety and Stress. It uses a likert scale. The scores indicate normal, mild, moderate, severe and extremely severe for each of the domains. The higher the scores, indicates the more severe the conditions.

Each of the three DASS-21 scales contains 7 items, divided into subscales with similar content. The depression scale assesses dysphoria, hopelessness, devaluation of life, self-deprecation, lack of interest / involvement, anhedonia and inertia. The anxiety scale assesses autonomic arousal, skeletal muscle effects, situational anxiety, and subjective experience of anxious affect. The stress scale is sensitive to levels of chronic non-specific arousal. It assesses difficulty relaxing, nervous arousal, and being easily upset / agitated, irritable / over-reactive and impatient. Scores for depression, anxiety and stress are calculated by summing the scores for the relevant items.

The DASS-21 is based on a dimensional rather than a categorical conception of psychological disorder. The assumption on which the DASS-21 development was based (and which was confirmed by the research data) is that the differences between the depression, anxiety and the stress experienced by normal subjects and clinical populations are essentially differences of degree. The DASS-21 therefore has no direct implications for the allocation of patients to discrete diagnostic categories postulated in classificatory systems such as the DSM and ICD. (Lovibond & Lovibond, 1995)

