### Sample size

Sample size was calculated using G\*Power 3.1 sample size calculator software. Based on reports by confidence score from a study analysing pre and post emergency department posting in junior doctors was used. The mean overall confidence score was 56.475(24.67) at the end of month 1 and 62.775(28.69) at the end of month 4(Williams et al., 1997). The estimated sample size was 208 participants after accounting for power of 80%, significance level of 0.05% and 30% attrition.

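### The written referral commitment names depression and anxiety but not stress, so a severe stress grade on its own is not covered

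*Combined protocol and SAP*

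**What the plan says.** Under Ethical considerations, the protocol describes the risk to participants as close to nil and then adds one qualification: "should the DASS score be suggestive of depression or anxiety, team members of the research team will refer the participant appropriately". No cut-off or severity grade is attached.

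The instrument is described under Secondary outcome, item b. The DASS covers three domains: depression, anxiety and stress. Each has its own total: "Scores for depression, anxiety and stress are calculated by summing the scores for the relevant items". Each also has its own severity grade: "The scores indicate normal, mild, moderate, severe and extremely severe for each of the domains".

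The DASS is completed twice. It is part of the baseline questionnaire, and it is repeated in the telephone interview one month after the participant starts work (Instruments & Data Collection; Data collection). The questionnaire given on the last day of the course does not include it.

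The Background section states the study's purpose as finding out whether the course is effective against house officer stress.

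**The concern.** The instrument grades three domains and the safety commitment responds to two. The one left out is the domain the study is about. The literature review ties high stress to as much as a threefold effect on thoughts of quitting. It also attributes the 1.2% of house officers who were terminated or quit in 2016 to inability to cope with stress. The section on the impact of stressed house officers links high stress, together with depression, to a lower standard of care.

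The team will therefore hold a graded stress score on identifiable people, and the second score is taken one month into a job that the protocol itself describes as stressful. If the written commitment is followed to the letter, a severe or extremely severe stress grade standing alone calls for no action. What is at stake is participant safety. The sample size, error rates and estimates are not affected.

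**Working it through.** No arithmetic applies, and the plan states no figure to reproduce. The check is a comparison of the relevant sections.

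1. **What the instrument yields.** Secondary outcome, item b: three domain scores, each summed from its own items and each graded from normal to extremely severe. Stress has its own content (trouble relaxing, nervous arousal, irritability, impatience), distinct from that of the other two scales. A high stress grade with normal depression and anxiety grades is therefore a possible result.

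2. **What triggers referral.** Ethical considerations: a score pointing to depression or to anxiety. The trigger is not a raised DASS score in general; it names the conditions the score must suggest. On the protocol's own definitions, the result in step 1 does not meet it.

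3. **Whether another section closes the gap.** I looked through the rest of the available text for any other referral, escalation or distress rule and found none. Two items under Intervention could be mistaken for one. The mention of referring cases is course teaching about patients. The plan to "guide them into different whatsapp groups according to their place of work for additional support" is peer networking arranged by workplace and is not tied to any score.

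4. **Whether a reason is given for leaving stress out.** None is stated. The closest text is the caution that "The DASS-21 therefore has no direct implications for the allocation of patients to discrete diagnostic categories", but this concerns the whole instrument. It applies equally to the depression and anxiety scales, which do trigger referral.

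5. **Whether the size can be computed.** It cannot. The input needed is the share of participants with a severe stress grade and normal depression and anxiety grades, and the documents do not give it. The literature review reports "the level of stress to be 34% in Kuala Lumpur and as high as 58% in Kota Kinabalu", but without a severity grade and without the share who had stress alone. The planned numbers (208 under Sample size, 260 in the Budget) do not supply the missing share.

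**The case against.** The strongest reply is that this is a defensible clinical choice. Depression and anxiety are recognised grounds for referral, while the protocol says of stress: "The stress scale is sensitive to levels of chronic non-specific arousal". A raised stress score alone may well be less urgent than a raised depression score. This has some force. It is a good reason to set a higher bar for stress, but a weaker reason for no commitment at all at the severe end, and the protocol does not itself make the argument.

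A second reply is that the sentence is a loose, discretionary promise and not an algorithm. It sets no threshold for any domain, does not say that only these conditions count, and leaves the team free to refer for stress. All of that is correct. A reader might infer that severely stressed participants would go unreferred, or that the protocol rules out helping them. The documents support neither inference. They show only that the written commitment does not extend that far.

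Third, the consent pages were removed before review, and participant information is a natural place for wording on distress. That stands, and it limits the claim to the text available.

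Finally, a reader might take the 34% to 58% stress rates as the proportion left without protection. They are not. They carry no severity grade, and they do not exclude people who would already be referred for depression or anxiety. The same rates are a reason not to add stress to the trigger without a cut-off, since that could generate many referrals for mild scores.

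**Conclusion.** The point holds as a gap in a stated safeguard: the commitment is narrower than the instrument it relies on, and the domain left out is the one the study targets. It is an omission and not a contradiction between sections. Its size cannot be quantified from the documents and may be near nil. It has no bearing on any outcome definition, estimate or test.

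The conclusion rests on two assumptions: that the sentence is read as written, and that no wider wording exists in the removed consent pages. Severity: minor. It is best treated as a cheap improvement to participant safety.

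**What to change.** First check whether the consent text already commits to referral for stress. If it does, bring the Ethical considerations section into line with it. If it does not, leave the depression and anxiety trigger exactly as it is and add a clause such as: or a stress score in the severe or extremely severe range. State that the commitment applies to the DASS at baseline and at the 1-month call. The protocol does not print the numerical limits of the severity grades, so the investigators should specify them and have the ethics committee confirm the wording.

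The cost is one clause and no new data, because the stress score is already collected and graded. Some extra referrals would follow. Their number cannot be computed, but it should be small, because the clause is confined to the top two grades and anyone already referred for depression or anxiety adds nothing. The analysis stays as planned.

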#### **Data Analysis**

The data will be analysed using IBM Social Package for Social Science (SPSS) version 24. A descriptive analysis of the demographic characteristics of the participants, clinical experience and baseline level of confidence, readiness and psychological wellbeing will be reported using means and standard deviations (SD) or median and inter-quartile range (IQR) for continuous variables (depending on the data distribution) and as frequencies and percentages for categorical data. An analysis to compare between participants who completed and withdrew from the study will be made using Chi-square or Exact test (for unbalanced data) for categorical variables and independent t-test for continuous data.

A repeated measures ANOVA will be conducted to determine the effectiveness of the intervention within the groups across the study periods (baseline, immediately after intervention and at 1 month after working). Controlling for baseline measures will be done to determine the change over time on the measured outcomes (level of confidence, readiness and psychological wellbeing). All analyses conducted are two-tailed with significant level set at p value <0.05.

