## Specific

- To determine the socio-demographic and past clinical experience of participants attending Medicorp's HO Preparatory Course
- 2. To determine the level of confidence, readiness, and psychological well-being of participants to work as a HO before attending the Medicorp HO Preparatory course
- 3. To determine the level of confidence and readiness of participants to work as a HO after immediately attending the Medicorp HO Preparatory course
- 4. To determine the level of confidence, readiness and psychological well-being of participants to work after 1 month working as a HO
- To determine the effectiveness of the Medicorp HO Preparatory course on the level of confidence, readiness and psychological well-being before attending the course and after 1 month working as a HO
- 6. To determine the determine the effectiveness of the Medicorp HO Preparatory course on the level of confidence and readiness immediately after attending the course

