## **Study Design:**

This is a pre-post quasi-experimental study that will be conducted over 12 months duration. Participants in this study will undergo a House Officer (HO) preparatory course. The level of confidence, readiness and psychological wellbeing will be evaluated. There will be three assessment time points: at baseline (before the course), immediately after the course (only for level of confidence and readiness) and 1 month after working as HO. This study is unable to have a control because of constraints in resources.

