### Study outcome measures:

### 1. Primary outcome

a. Level of confidence:

This will be adapted from the IMU Student Competency Survey (Appendix 2) as there are no published studies on the confidence level of medical graduates before beginning HO-ship. The questionnaire comprises of 5 sections. The first 4 sections asses on generic skills, practical tasks, soft skills and their confidence as a whole, using a Likert scale assessment. Scoring is a mean score of 1-5 and the higher the score, the higher the confidence. The last section asks on the one daunting aspect of being a HO out of a list of 7 things, this section is descriptive.

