### **Instruments & Data Collection**

### Intervention: The Medicorp HO Preparatory Module

### Tools for assessment:

### 1. Baseline questionnaire

The study instrument will be a set of questionnaire that will be divided into sections A-E.

The English versions will be used.

a) Socio-demographic data :

This will include certain details of participants such as:

- Age
- Sex
- Religion
- Ethnicity
- Year of graduation
- University of Graduation
- Marital status
- Place of work (evaluation during 1 month post HO-ship)

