## 2. Post course questionnaire (immediate)

- a) Level of confidence
- b) Readiness

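### The three-visit repeated-measures ANOVA has no missing-data method and no named contrast; as normally run it drops people who miss the 1-month call from the immediate effect

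*Combined protocol and SAP*

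**What the plan says.** The Data Analysis section states: "A repeated measures ANOVA will be conducted to determine the effectiveness of the intervention within the groups across the study periods", and lists the periods as baseline, immediately after the intervention and 1 month after starting work. The software is SPSS 24 and tests are two-sided at 0.05. A further sentence says that baseline measures will be controlled for, without naming covariates or a model. Dropouts appear only in a comparison of those who completed with those who withdrew.

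The specific objectives set two separate effectiveness comparisons. Objective 5 concerns confidence, readiness and psychological well-being "before attending the course and after 1 month working as a HO". Objective 6 concerns the effect "on the level of confidence and readiness immediately after attending the course". Confidence is the only outcome listed as primary.

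Confidence and readiness are measured at all three visits. DASS is measured at baseline and 1 month only (Study Design; Post course questionnaire; Case report form). The end-of-course form is completed on the last course day, and the 1-month scores are collected by telephone (Data collection). The Sample size section arrives at 208 participants, citing 80% power and "significance level of 0.05% and 30% attrition".

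**The concern.** Objective 6 needs two scores, both collected on site within one short course. The third score depends on reaching a newly employed doctor by telephone some time later. A classical repeated-measures ANOVA needs one complete row per person, so a missed call removes that person's baseline and end-of-course scores too. The comparison of completers with withdrawers describes this loss but does not change the estimate.

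In a study without a control group the pre-post contrasts are the whole of the effectiveness evidence, so it matters that they use the data collected and are fixed in advance. The overall F-test says only that the three means are not all equal; by itself it answers neither objective 5 nor objective 6. Nothing says which of the two confidence comparisons decides whether the course is judged effective.

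**Working it through.** **Inputs.** From the Sample size section: means 56.475 and 62.775 (difference 6.30), SDs 24.67 and 28.69, power 80%, attrition 30%, N = 208. From the Data Analysis section: two-sided 0.05. The correlation between visits, r, is not given; 0.5 is assumed and varied.

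**Reproducing the 208.**
- SD of change = √(24.67² + 28.69² − 2 × 0.5 × 24.67 × 28.69) = 26.91.
- Standardised change = 6.30 / 26.91 = 0.234.
- A two-sided paired t-test at 0.05 with 80% power needs 146 people; 146 / 0.7 = 208.6, which matches 208.
- Reading the printed 0.05% literally (0.0005) would give 496, so 0.05 is used here.

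The sample size therefore corresponds to one paired comparison, with attrition already allowed for.

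**Precision of the immediate effect.** 208 × 0.7 = 145.6, so about 145 people would have all three scores. The 6.30-point difference comes from months 1 and 4 of an emergency posting; applying it to the immediate effect is an assumption. Half-width = t(0.975, n−1) × 26.91 / √n.

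| Scores used for objective 6 | n | Power | 95% CI half-width |
|---|---|---|---|
| Completers only | 145 | 80% | 4.4 points |
| All pairs, 20% lost by course end | 166 | 85% | 4.1 |
| All pairs, 10% lost by course end | 187 | 89% | 3.9 |
| All pairs, none lost by course end | 208 | 92% | 3.7 |

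If all 30% are lost before the course ends, there is nothing to recover. At r = 0.3 the extremes are 66% and 81%; at r = 0.7 they are 95% and 99%.

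**Bias in the completer estimate.** This was simulated with a true immediate gain of 6.30 / average SD = 6.30 / 26.68 ≈ 0.235 SD. Assumptions: 30% lost after the course, low scorers more likely to be lost, and a logistic model with odds ratios (OR) of 1.2, 1.5 and 2 per SD. SDs are equal and all correlations 0.5 unless stated.

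| Loss follows | OR 1.2 | OR 1.5 | OR 2 |
|---|---|---|---|
| Baseline score | 0.208 | 0.177 | 0.140 |
| End-of-course score | 0.263 | 0.294 | 0.330 |
| 1-month score, equal SDs and correlations | 0.235 | 0.235 | 0.235 |
| 1-month score, correlating 0.5 with end of course, 0.3 with baseline | 0.245 | 0.258 | 0.273 |
| 1-month score, correlating 0.4 with end of course, 0.6 with baseline | 0.223 | 0.214 | 0.197 |
| 1-month score, larger SD (28.69) after baseline | 0.240 | 0.245 | 0.248 |

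The sign depends on who is lost. Loss that follows only the 1-month score is harmless to the immediate effect only in the symmetric case; otherwise it gave about 0.20 to 0.27.

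**DASS and baseline control.** DASS has no end-of-course score, so a three-period ANOVA cannot be fitted to it, and no two-visit analysis is written down. The baseline outcome is already one level of the ANOVA, so controlling for baseline measures either repeats it or refers to covariates that are not named.

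**The case against.** **The plan does not specify listwise deletion.** True. The point rests on how this ANOVA is normally run and on the absence of any stated alternative. A reader should not infer that the plan has chosen complete cases.

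**Attrition is already allowed for.** True. A reader might infer that the study is underpowered; the arithmetic does not support that, because about 145 completers still give 80%.

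**The 80% against 92% contrast is conditional.** It needs r = 0.5, the full 30% lost, all of it after the course, and a borrowed effect size. With a 10-point immediate gain, 145 completers would already give 99%. The 30% is an allowance, not an observed rate. The plan also has retention measures: placement tracking, workplace message groups and RM50 tokens. Its budget covers 260 participants; at 70% retention that is 182 completers and 88% power. These points limit the size of the problem but do not say how a missing score will be handled.

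**Objectives 5 and 6 and the primary outcome are already declared.** This also stands. A reader might infer a free choice among outcomes; what is open is only which of two declared confidence comparisons is decisive.

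**The mixed model is not better in every case.** Correct for the 1-month contrast. If 30% loss follows the unseen 1-month score (OR 1.5 to 2), the mixed model gives 0.31 to 0.37 against 0.29 to 0.33 for completers, with a true value of 0.235. If loss follows the baseline score (OR 1.2 to 2), it gives 0.235 against 0.14 to 0.21.

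**Conclusion.** The point holds in a limited form and should be corrected before analysis. The stated model, as normally run, discards usable pairs for objective 6. The cost is precision, at most about 80% against 92% power under the assumptions above, and less with smaller or earlier loss. There may also be bias: a true 0.235 SD gain could appear as 0.14 to 0.33 if 30% late loss follows baseline or end-of-course score. The sign is unknown, and there is no bias if loss is unrelated to scores. The documents do not show that the immediate effect will be biased; they only leave it unprotected. The missing contrasts and the missing two-visit DASS analysis follow directly from the text and need no assumption.

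**What to change.** In the Data Analysis section:

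1. Replace the ANOVA with a linear mixed model (SPSS MIXED; visit as a fixed effect, unstructured within-person covariance, all available observations). Use three visits for confidence and readiness, and two (baseline, 1 month) for each DASS-21 scale.
2. Pre-specify end of course minus baseline (confidence, readiness) and 1 month minus baseline (all outcomes), with 95% CIs. Before analysis, name one of the two confidence contrasts as primary at two-sided 0.05 and make the rest secondary.
3. Name the covariates meant by controlling for baseline measures, or delete that sentence.
4. Report the number with data at each visit.
5. Add a sensitivity analysis for the 1-month contrast, shifting it by (share without a 1-month score) × delta in both directions, for example delta from −0.5 to +0.5 SD. This range is assumed. With 30% missing the shift is up to 0.30 × 0.5 = 0.15 SD either way. In the worst mixed-model case above the shift needed is 0.366 − 0.235 = 0.131 SD, that is delta = 0.131 / 0.30 = 0.44 SD.

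The minimum alternative is paired comparisons on all available pairs. These match the mixed model for the immediate effect only if loss before course end is nil or unrelated to scores. If that early loss follows the baseline score (OR 1.2 to 2), pairs give about 0.20 to 0.23 at 10% loss and 0.17 to 0.22 at 20%.

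The cost is wording and slightly more modelling, in software already named, with no new data. Naming one primary contrast costs no power. The drawback is the 1-month weakness described above, which the sensitivity analysis is there to expose.
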